#### 4.7.3 Secondary Endpoints - Immunogenicity

The humoral immune response will be assessed in terms of HI antibodies for both Seqirus QIV and the QIV comparator. Serum HI antibody titers against the 4 influenza vaccine strains will be used to calculate:

- GMTs: Geometric mean of HI titers pre-vaccination (Day 1) and post-vaccination (Study Exit Visit);

- SCRs: Percentage of subjects with either a pre-vaccination HI titer < 1:10 and a post-vaccination HI titer  $\geq$  1:40 or a pre-vaccination titer  $\geq$  1:10 and a  $\geq$  4-fold increase in post-vaccination titer;
- The percentage of subjects with a titer  $\geq$ 40 (seroprotection rate) at Day 1 and at Study Exit Visit;
- Geometric mean fold increase (GMFI)\*: Geometric mean fold titer rise from Day 1 to Study Exit Visit

*\*GMFI in antibody titer is defined as the geometric mean of the fold increase of post-vaccination HI antibody titer over the pre-vaccination HI antibody titer.*

For each treatment group (each age strata as well as overall) summary tables, by strain, will be presented for GMT (mean and 95% CIs), number and percentage of subjects with a titer  $\geq$ 40 at Day 1 and Study Exit Visit, Day 29, SCR (number and percentage of subjects at Study Exit Visit) and GMFI (mean and 95% CIs).

All secondary immunogenicity endpoint summaries described above will be presented overall, and by age strata, by gender, by race, and by ethnicity.

The distribution of antibody titers 6 through 35 months of age, 36 through 59 months of age, as well as overall (for each vaccine) will be displayed graphically using reverse cumulative distribution (RCD) curves. RCD curves following the first and second vaccinations will also be displayed by age strata.

#### **4.7.3.1 Influenza-Like-Illness**

For influenza-like illness the number and percentage of subjects experiencing at least one episode will be presented with 95% CIs. The relative risk and 95% CI based on unconditional exact method will also be presented for Seqirus QIV/Comparator QIV. P-value for Cochran Mantel Haenszel test for general association will be also reported. Analysis will be performed using the Full Analysis Set.

Influenza-like illness will be obtained from 'Did subject experience fever and at least 1 other influenza-like symptom?'

Laboratory results will be listed.

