Postvaccination Safety Follow-up Telephone Call (Day 90+7 and 180+7 after Last Vaccination)

Serious adverse event and AESI information will be collected for a total of 180 days (180+7 days) after administration of the last dose of study vaccine:

Unscheduled Visit - Influenza-like Illness (ILI) Visit

Subjects reporting signs/symptoms of an ILI between Visit 1 and Study Exit Visit (Visit 2 or Visit 3) will be asked to attend an additional clinic visit within 72 hours of the symptoms meeting the case definition of an ILI, for confirmation of the ILI.

The criteria for an ILI are as follows:

- Elevated axillary temperature of $\geq 99.5^{\circ}\text{F}$ ($\geq 37.5^{\circ}\text{C}$) or a clear history of fever or chills); and

- At least one respiratory symptom: including sore throat, cough, wheezing, rhinorrhea/rhinitis; and
- At least one systemic symptom, including myalgia, headache, malaise and fatigue, nausea and/or vomiting, diarrhea, loss of appetite and irritability.

Upon confirmation that the ILI case definition is met, the subject's temperature will be assessed and attempts will be made to diagnose influenza viral infection by obtaining nasal and throat swab specimens. These will be analyzed for laboratory confirmation of influenza A and/ or B by Reverse Transcriptase Polymerase Chain Reaction (RT-PCR).

Unscheduled Visit – Cellulitis-like Reaction

Subjects reporting signs/symptoms of a Cellulitis-like Reaction between Day 1 and Study Exit Visit will be asked to attend an additional clinic visit within 24 hours (up to 3 days if on a weekend) of the symptoms meeting the definition of a Cellulitis-like Reaction.

The criteria for a Cellulitis-like Reaction are concurrent presence of all three of the following:

- Grade 3 injection site pain;
- Grade 3 injection site erythema;
- Grade 3 injection site induration.

Investigational site staff will assess for the presence of ulceration, abscess, or necrosis at the injection site.

Efficacy Assessments

Efficacy assessment involves the assessment of immunogenicity on the basis of HI antibody titer to each strain. Immunogenicity will be expressed as:

- *HI antibody titer for each strain.* All analyses involving HI antibody titer (namely GMT within a treatment group) will be based on the log scale and the resultant summary statistic back-transformed to derived GMT;

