Subjects reporting signs/symptoms of an ILI between Visit 1 and Study Exit Visit (Visit 2 or Visit 3) will be asked to attend an additional clinic visit within 72 hours of the symptoms meeting the case definition of an ILI, for confirmation of the ILI.

The criteria for an ILI are as follows:

- Elevated axillary temperature of  $\geq 99.5^{\circ}\text{F}$  ( $\geq 37.5^{\circ}\text{C}$ ) or a clear history of fever or chills; and
- At least one respiratory symptom, including sore throat, cough, wheezing, rhinorrhea/rhinitis; and
- At least one systemic symptom, including myalgia, headache, malaise and fatigue, nausea and/or vomiting, loss of appetite, and irritability.

To qualify as symptoms for the ILI case definition, symptoms should be either new, or for chronic symptoms, changed in severity or nature.

Influenza antiviral drugs (Symmetrel [amantadine], rimantadine, Tamiflu [oseltamivir] or Relenza [zanamivir]) should not be prescribed from any source until after the ILI assessment visit and the collection of respiratory specimens if indicated.

The site should perform an assessment to attempt to confirm a postvaccination ILI at the time of the ILI-assessment visit (the subject's temperature and clinical symptoms should be assessed). Additionally, the site may also confirm a postvaccination ILI through review of the AE diaries and/or illness history reported verbally by the subject at a time prior to the ILI visit. Information related to confirmation of a postvaccination ILI should be recorded in the subject's source notes.

Upon confirmation that the ILI case definition is met, the subject's temperature will be assessed and attempts will be made to diagnose influenza viral infection by obtaining nasal and throat swab specimens. These will be analyzed for laboratory confirmation of influenza A and/or B by Reverse Transcriptase Polymerase Chain Reaction (RT-PCR).

Laboratory confirmation is more likely for specimens collected within approximately 3-4 days of illness onset, but nasal and throat swabs should be collected if the ILI assessment visit occurs up to 7 days after illness onset, to try to identify as many cases of laboratory confirmed influenza infection as possible. After 7 days following illness onset, the Investigator may choose whether to collect nasal and throat swabs, based on their clinical judgement of the potential value of testing specimens due to ongoing ILI symptoms.

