### 3.3.4 Schedule of Assessments

Schedule of Assessments – Single Dose Regimen						
Assessment	Pre-Study	Visit 1	Phone call	Visit 2	Phone call	Phone call
	Day -7 to -1	Vaccination	Diaries Reminder	Exit Visit	SAE Follow-up	SAE Follow-up
	Day -7 to -1	Day 1	Day 3 + 2	Day 29 + 4	Day 90 + 7	Day 180 + 7
Invitation to participate		✓ 				
Informed consent		✓ 				
Demographics and influenza vaccination history		✓ 				
Medical history and baseline medication use		✓ 				
Targeted physical examination (if necessary)		✓ 		✓		
Body weight		✓ 				
Axillary temperature		✓				
Review of eligibility criteria		✓				
Blood sample for immunogenicity testing		✓		✓		
Vaccination		✓				
Provision of study supplies and instructions		✓				
Solicited Diary review			✓	✓		
Unsolicited/Concomitant Medications Diary review			✓	✓		
Assessment for cellulitis-like reaction, influenza-like illness (if applicable) 		← ✓ →				
Review of adverse events and concomitant medications	← ✓ →					
Review of SAEs (if applicable)	← ✓ →					

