**Notes to the schedule of assessments:**

 These may be performed on or up to 7 days before the day of vaccination.

 Elevated axillary temperature of  $\geq 99.5^{\circ}\text{F}$  ( $\geq 37.5^{\circ}\text{C}$ ) (or a clear history of fever/chills), and at least one respiratory symptom (including sore throat, cough, wheezing, rhinorrhea/rhinitis) and at least one systemic symptom (including myalgia, headache, malaise, nausea and/or vomiting, loss of appetite, and irritability).

Schedule of Assessments – Two Dose Regimen

Assessment		Visit 1	Phone call	Visit 2	Phone call	Visit 3	Phone call	Phone call
	Pre-Study	Vaccination	Diaries Reminder	Vaccination	Diaries Reminder	Exit Visit	SAE Follow-up	SAE Follow-up
	Day -7 to -1	Day 1	Day 3 + 2	Day 29 + 4	Day 3 + 2 after 2 nd dose	Day 29 + 4 after 2 nd dose	Day 90 + 7 after 2 nd dose	Day 180 + 7 after 2 nd dose
Invitation to participate		✓ 						
Informed consent		✓ 						
Demographics and influenza vaccination history		✓ 						
Medical history and baseline medication use		✓ 						
Targeted physical examination (if necessary)		✓ 		✓		✓		
Body weight		✓ 						
Axillary temperature		✓		✓				
Review of eligibility criteria		✓		✓				
Blood sample for immunogenicity testing		✓				✓		
Vaccination		✓		✓				
Provision of study supplies and instructions		✓		✓				
Solicited Diary review			✓	✓	✓	✓		
Unsolicited/Concomitant Medications Diary review			✓	✓	✓	✓		
Assessment for cellulitis-like reaction, influenza-like illness (if applicable) 				✓				
Review of adverse events and concomitant medications				✓				
Review of SAEs (if applicable)					✓			

Notes to the schedule of assessments:  These may be performed on or up to 7 days before the day of vaccination.  Elevated axillary temperature of  $\geq 99.5^{\circ}\text{F}$  ( $\geq 37.5^{\circ}\text{C}$ ) (or a clear history of fever/chills), and at least one respiratory symptom (including sore throat, cough, wheezing, rhinorrhea/rhinitis) and at least one systemic symptom (including myalgia, headache, malaise, nausea and vomiting, loss of appetite, and irritability).

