### 3.5.2.3 Criteria for Defining Safety Populations

Follow-up safety data is defined as any safety information that is recorded for a subject in a Study Diary or in the subject's medical notes.

The following criteria will be used to define NO follow-up safety data (not included in the Overall Safety Population):

- “Were any unsolicited AEs experienced that were not recorded in the diary?” = BLANK (no entries) AND
- “Were any new SAEs reported?” (Day 90 & 180) = BLANK AND
- “Was the subject confirmed to have experienced symptoms meeting cellulitis-like reaction criteria?” = BLANK AND
- Any AE/SAE form = BLANK AND
- Unsolicited Diary Other Body Symptoms = BLANK (no entries) AND
- Solicited Diary Local Symptoms= BLANK (all 7 days after first and second vaccination) AND
- Solicited Diary Temperature= BLANK (all 7 days after first and second vaccination) AND
- Solicited Diary Systemic Symptoms = BLANK (all 7 days after first and second vaccination)
- Site Entered Local Symptoms = BLANK (all 7 days after first and second vaccination) AND
- Site Entered Temperature= BLANK (all 7 days after first and second vaccination) AND

- Site Entered Systemic Symptoms = BLANK (all 7 days after first and second vaccination)

The following criteria will be used to define subjects with follow-up safety data (included in the Overall Safety Population):

- “Were any unsolicited AEs experienced that were not recorded in the diary?” = YES OR
- “Were any unsolicited AEs experienced that were not recorded in the diary?” = NO OR
- “Were any new SAEs reported?” = YES (Day 90 & 180) OR
- “Were any new SAEs reported?” = NO (Day 90 & 180) OR
- “Was the subject confirmed to have experienced symptoms meeting cellulitis-like reaction criteria?” = YES OR
- “Was the subject confirmed to have experienced symptoms meeting cellulitis-like reaction criteria?” = NO OR
- Any AE/SAE form = ANY FIELD HAS DATA OR
- Unsolicited Diary Other Body Symptoms = ANY FIELD HAS DATA (on any of the 28 days) OR
- Solicited Diary Local Symptoms= ANY FIELD HAS DATA (on any of the 7 days after first or second vaccination) OR
- Solicited Diary Temperature= ANY FIELD HAS DATA (on any of the 7 days after first or second vaccination) OR
- Solicited Diary Systemic Symptoms = ANY FIELD HAS DATA (on any of the 7 days after first or second vaccination)
- Site Entered Local Symptoms= ANY FIELD HAS DATA (on any of the 7 days after first or second vaccination) OR

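### SAP 4.7.3.1 takes influenza-like illness from a form item that, as worded, does not match the study's three-part case definition; only supportive Table 14.2.6 is affected

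*SAP*

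**What the plan says.** **The analysis rule.** SAP 4.7.3.1 obtains ILI from the item "Did subject experience fever and at least 1 other influenza-like symptom". On the Full Analysis Set it reports the number and percentage of subjects with at least one episode, a Seqirus QIV/Comparator QIV relative risk with an unconditional exact 95% CI, and a Cochran-Mantel-Haenszel p-value. The output is Table 14.2.6.

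**The case definition.** SAP 3.3.3 requires an axillary temperature of at least 37.5 °C or a clear history of fever or of chills. It then requires "At least one respiratory symptom, including sore throat, cough, wheezing, rhinorrhea/rhinitis; and" and, as a third element, at least one systemic symptom. Footnote 2 to the schedules in SAP 3.3.4 repeats the structure: "and at least one respiratory symptom (including sore throat, cough, wheezing, rhinorrhea/rhinitis) and at least one systemic symptom". The protocol uses the same three parts in the synopsis ("At least one respiratory symptom: including sore throat, cough, wheezing, rhinorrhea/rhinitis; and"), in its schedule footnotes and in section 8.4.3.

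**The visit.** A child reporting ILI symptoms is asked to attend "within 72 hours of the symptoms meeting the case definition of an ILI, for confirmation of the ILI". SAP 3.3.3 adds: "Information related to confirmation of a postvaccination ILI should be recorded", in the source notes. The schedule row reads "Assessment for cellulitis-like reaction, influenza-like illness (if applicable"). SAP 4.7.3.1 does not refer to the confirmation step.

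**The concern.** A table should count what its title names. Here the stated derivation and the study's definition are different rules, and SAP 4.7.3.1 does not link them.

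The difference matters because of what else happens in the same weeks. Under SAP 4.7.4.2, solicited fever starts at 37.5 °C, the same threshold as in the ILI definition. Several solicited systemic events are also ILI systemic symptoms: nausea or vomiting at all ages, irritability and loss of appetite under 36 months, and headache, myalgia, and malaise and fatigue from 36 months. A toddler with post-vaccination fever and irritability but no respiratory symptom satisfies the item's words without being an ILI case.

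Table 14.2.6 carries a relative risk and a p-value. If such children are counted, part of any between-arm difference in reactogenicity, in either direction, could be read as a difference in illness.

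**Working it through.** The documents give no ILI rate, so there is no plan figure to reproduce. The check is a comparison of two rules, followed by an illustration on assumed inputs.

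**1. The two rules**

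- Item: fever AND (respiratory OR systemic symptom).
- Definition: (fever OR history of fever or chills) AND respiratory AND systemic symptom.

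| Pattern | Item | Definition |
|---|---|---|
| Fever + respiratory + systemic | yes | yes |
| Fever + respiratory only | yes | no |
| Fever + systemic only | yes | no |
| History of chills, no fever, + respiratory + systemic | no | yes |

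The mismatch runs both ways. For a history of fever without a measured temperature, the answer depends on how the respondent reads the item; chills alone are the clear miss.

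**2. Effect on the relative risk**

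Notation:
- p0: comparator-arm case rate; r: true relative risk.
- f0: comparator-arm rate of counted non-cases; k: ratio of non-case rates, Seqirus QIV over comparator.
- s1, s0: share of true cases that the item captures in the Seqirus QIV and comparator arms.

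Cases and non-cases are disjoint, so

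observed RR = (s1·r·p0 + k·f0) / (s0·p0 + f0) = (1 − w)·r·(s1/s0) + w·k, with w = f0/(s0·p0 + f0), the share of counted comparator-arm children who are non-cases.

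Consequences:
- If only confirmed cases are counted and none is missed (w = 0, s1 = s0 = 1), the RR is unchanged.
- If cases are missed equally in both arms (s1 = s0), events are lost but this term does not move the RR. If they are missed unequally, the true-case part is multiplied by s1/s0, which can be above or below 1.
- If non-cases are counted (w > 0), the RR is pulled towards k.

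Illustration with s1 = s0. All inputs are assumed; none comes from the documents:

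| Assumed true RR, k | w = 10% | w = 25% | w = 50% |
|---|---|---|---|
| r = 0.60, k = 1 | 0.64 | 0.70 | 0.80 |
| r = 1, k = 1 | 1.00 | 1.00 | 1.00 |
| r = 1, k = 1.5 | 1.05 | 1.13 | 1.25 |
| r = 1, k = 2/3 | 0.97 | 0.92 | 0.83 |

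Example: 0.75 × 0.60 + 0.25 × 1 = 0.70.

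**3. Scale against sampling error**

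The planned 2222 subjects at 3:1 give about 1667 and 555. Around RR = 1, a log-Wald interval (an approximation to the SAP's exact one) uses SE = √(1/a − 1/1667 + 1/b − 1/555), with a and b the expected events:

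| Assumed ILI rate | a, b | 95% CI |
|---|---|---|
| 2% | 33.3, 11.1 | 0.51 to 1.96 |
| 5% | 83.4, 27.8 | 0.66 to 1.52 |
| 10% | 166.7, 55.5 | 0.75 to 1.33 |

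Every shift from RR = 1 illustrated above lies inside all three intervals.

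**4. What depends on the item**

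ILI is not among the endpoints in SAP 2.1.2, 2.2.2 or 2.3.2, although 4.7.3.1 sits under the secondary immunogenicity heading. The Evaluable Population (SAP 3.5.3), and hence the Per-Protocol Population drawn from it, excludes on laboratory-confirmed influenza, not on this item.

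**The case against.** The strongest reply is that the form is not in the documents. The only ILI pathway described is an unscheduled visit after symptoms meet the definition, and the schedule marks the assessment as applicable only to some children. Nothing says that the item is put to every child. If it is answered only once the definition is confirmed, the table is right as it stands.

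That limits the consequence but does not remove the mismatch. No passage restricts the item to confirmed cases. The visit is itself held for confirmation, so a child who attends and is not confirmed could still satisfy the item.

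Three stronger inferences are tempting, and the documents support none of them:

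- *The table will count non-cases.* This depends on who answers the item, which is not stated. The cellulitis item in SAP 3.5.2.3, "Was the subject confirmed to have experienced symptoms meeting cellulitis-like reaction criteria", is worded to confirmed criteria. It is quoted there to define safety populations, and says nothing about how the ILI item is completed.
- *The relative risk will be diluted towards 1.* That is one of two possible errors. The item can also miss cases, and a reactogenicity difference could move the ratio either way. Moreover, only the fever-plus-systemic group overlaps reactions. If that group were half of the non-cases and the rest were balanced, an overall k of 1.5 would need a twofold ratio within it (0.5 × 2 + 0.5 × 1 = 1.5).
- *The non-inferiority conclusion is exposed.* It is not, because neither the co-primary analyses nor their populations use this item.

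It is also fair to say that the protocol plans no ILI incidence analysis, so no protocol-defined estimate is altered. RT-PCR results are listed separately in any case.

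**Conclusion.** The point stands as a minor one. The written derivation contradicts the study's own definition in two directions: it can admit children with only one symptom type, and it can omit children who qualify through history, most clearly those with chills and no fever. That conclusion rests on the wording alone and is firm.

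The effect on Table 14.2.6 is not established. Its size and direction are unknown, the illustrated shifts rest wholly on assumed inputs, and the effect is nil if the item is completed only for confirmed cases. Whatever the effect, it is confined to one supportive table.

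Two side matters are documentation only. Protocol section 11 plans no between-arm ILI comparison, and SAP 4.13 does not list the one that the SAP adds; since the protocol leaves the full description of the analyses to the SAP, whether this must be logged as a change is arguable. The SAP's systemic symptom lists omit diarrhea, which the protocol names; both lists are introduced as non-exhaustive, but the passages should be reconciled.

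**What to change.** In SAP 4.7.3.1, before the interim unblinding, count a subject as having ILI for Table 14.2.6 only when all three parts of the definition are met, including the history alternative for the fever element. Use the site's confirmation or the recorded component symptoms.

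- If the form already restricts the item to confirmed cases, one sentence saying so is enough.
- If neither source is in the database (the documents do not say), label the table as using the broader item. Retrieving confirmations from source notes is possible, but may be more work than one supportive table justifies.
- List the added between-arm comparison in SAP 4.13, and align the symptom lists.

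The cost is one sentence or one derived variable. The strict rule may leave fewer events and a wider interval. Some overlap with vaccine reactions will remain, because the ILI window opens at Visit 1.

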#### **4.7.4 Secondary Endpoints - Safety**

AEs will be monitored after vaccination as per the following;

- Frequency and severity of solicited local adverse reactions and systemic adverse events (AEs) for 7 days (ie, day of vaccination and 6 subsequent days) after each vaccination dose;
- Frequency of cellulitis-like reaction for at least 28 days after each vaccination dose;
- Frequency and severity of unsolicited AEs for at least 28 days (ie, day of vaccination and 27 subsequent days) after each vaccination dose;
- Frequency of serious adverse events (SAEs) for at least 180 days after the last vaccination dose.

#### 4.7.4.1 Total Adverse Events

The total number of AEs (including solicited and unsolicited AEs, SAEs, and AESIs) will be summarised by treatment (i.e. Seqirus QIV/Comparator QIV/Overall), by presenting the number and percentage of subjects having one or more events, and the relationship and severity of each event. Each summary will be presented for total AEs, solicited local AEs, solicited systemic AEs, and unsolicited AEs. The number of subjects with an SAE or AESI, a related SAE or AESI, who discontinued due to an AE or an SAE or an AESI, or had an SAE resulting in death, will also be presented. Summaries will be repeated by Age Strata, Gender, Race, and Ethnicity.

Related events are defined as events that are related to study medication or with an unknown relationship.

An adverse event of special interest [AESI] is one of scientific and medical concern specific to the sponsor's product or program, for which ongoing monitoring and rapid communication by the investigator to the sponsor can be appropriate. Such an event might warrant further investigation in order to characterize and understand it.

AESIs include the following:

AESI	Preferred Term
Bell's Palsy	VIIth nerve paralysis
Encephalomyelitis	Encephalomyelitis
Guillain-Barre Syndrome	Guillain-Barre Syndrome
Optic Neuritis	Optic Neuritis
Thrombocytopenia	Thrombocytopenia
Transverse Myelitis	Myelitis transverse
Vasculitis	Vasculitis
Demyelinating disorders	Acute disseminated encephalomyelitis (ADEM) Encephalomyelitis Acute haemorrhagic Leukoencephalitis (AHL) Acute hemorrhagic encephalomyelitis (AHEM) Acute necrotizing hemorrhagic leukoencephalitis (ANHLE) Leukoencephalitis Multiple sclerosis Primary progressive multiple sclerosis Progressive multiple sclerosis Progressive relapsing multiple sclerosis Relapsing-remitting multiple sclerosis Neuromyelitis optica (NMO) Chronic inflammatory demyelinating polyradiculoneuropathy (CIDP) Demyelinating polyneuropathy Lewis-Summer syndrome
Febrile convulsion	Febrile convulsion
Febrile delirium	Delirium febrile

